**Table 5. Sample**

Condition Category	Diagnoses	N	Peer Coach
1. Frequent Hospitalizations or ED visits	Sickle Cell Disease; Chronic Kidney Disease, Lupus	50 PICASO 25 control	4-5
2. High daily management with intermittent flares	Type 1 Diabetes Mellitus; Inflammatory Bowel Disease; Severe Asthma	70 PICASO 35 control	5 -6
3. Survivor of life-threat condition requiring ongoing symptom mgmt	Stem Cell Transplant, Organ Transplant, Cancer Survivor	30 PICASO 15 control	3-4
Total: 150 PICASO / 75-control 2:1 ratio			12-15

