Randomization and data collection (detail in [Human Subjects and Clinical Trials Information Section 4.2.a.7 & 4.2.a.11](#)): On completion of baseline data collection, AYAs will be randomized using a stratified randomization with permuted block sizes of four to either the PICASO intervention (N=150) or attention control group (N=75). While stratifying on condition category, a 2:1 treatment allocation will be applied to ensure as an intervention sample size that is sufficient to provide robust findings and increase the precision of the outcome parameter estimates for the PICASO intervention. A RedCAP data base platform will be used to administer the randomization scheme prepared by the study statistician.

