Peer coach recruitment and training ([details in Human Subjects and Clinical Trials Information Sections 4.3.a](#)): Peer coaches are young adults (18-26 years) with a COCC who have been identified by clinic staff (attending physicians, fellows, nurse practitioners) as having exemplary activated self-management skills and, based upon their interpersonal skills, having the potential to be trained as a peer coach. Those young adults who are recommended will undergo a screening process and interview by the study investigators ([name], [name], [name]). If they express interest in training and employment as a peer coach they will be hired and trained following the training protocol described below. We plan to employ 12- 15 peer coaches who represent the condition categories (see Table 5). Peer coaches will receive training from Co-I [name] (Coach Supervisor) using a health and wellness curriculum designed by [name] who is an Integrative Health Coach, and previously tested by the study investigators. Training is composed of a five-day program and ongoing semi-monthly supervisory sessions. Training content includes a review of the coaching framework including social support and self-determination theories, motivational interviewing techniques and information about health behavior change. Training sessions focus on the coach-AYA relationship and use of motivational interviewing techniques. Various role-playing sequences are used throughout the training program to provide coaches with the opportunity to test their skills. Semi-monthly supervisory sessions will be conducted with coaches and the research team including continued education and support. Supporting AYAs with a similar condition as oneself can be emotionally distressing at times, and both [name] who is a licensed pediatrician and pediatric psychiatrist, and [name], LCSW who is a licensed clinical social worker, can consult and refer coaches experiencing problems.

[figure not shown]

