Figure 2 identifies characteristics of the AYA that are known to be related to the development of independent self-management. The intervention is designed to address a range of these characteristics and to have flexibility to support AYAs based on known variations. For example, the intervention can be tailored so that younger AYAs receive support targeting earlier stages of the development of activation and self-management. Each AYA will be matched with a coach, based on membership in 1 of 3 condition categories (see Table 5), who will provide support using the InquisitHealth Mentor 1:1™ Web Based Portal mobile telephone/text platform and the curriculum that guides them to assess AYA goals and provide support in addressing these goals.

To enact the four key functions of peer support, the coaches develop a relationship over time with their assigned AYAs. The first phase of the intervention involves an assessment and goal setting call during which the peer coach learns about the AYA's experience with their COCC, how they view their current self-management skills and how they envision their ideal health in adulthood. Through this initial call the coach and AYA will identify specific goals to work towards their vision of health. Throughout the process of coaching, the coach and AYA identify action steps towards the health and self-management goals, draw upon the AYA's strengths and existing skills, examine potential barriers to successful progression towards their goals and develop plans for addressing those barriers. The curriculum for the intervention is nondirective but allows coaches to help AYAs identify areas to work on within the four domains of self-management – knowledge, partnership in treatment, recognition/management of symptoms, and coping – as they relate to the AYA's personal health goals and vision for their future. Table 1 provides examples of the ways in which a peer coach would provide support to an AYA participant utilizing a nondirective approach.

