In general, calls last 20-30 minutes. During the first call, the coach and AYA have the opportunity to learn about one another's experiences with living with a chronic condition. During subsequent calls, the coach focuses primarily on the specific sub-behavior elected by the AYA. The coaching process model described in figure 2, helps the coach guide behavior change, beginning with assessing the participant's vision for the future, establishing focus, readiness to change, and then pursuit and maintenance of identified goals. As goal progress is made, the coach and AYA work to identify a new goal, or in the case of no progress, they discuss barriers and strategies, with an option to move on to another goal. Between sessions the coach and participant can exchange text messages including an update on progress towards a goal. At the end of the intervention the final call involves an opportunity for closure and for the coach and AYA to review progress on goals and future steps.

Attention Control: Over 12 months the attention control group participants will receive a monthly electronic newsletter with educational content about COCC management and the differences between pediatric and adult health care systems, as well as a monthly phone call from study staff to ensure receipt of the newsletter and to answer questions regarding content, and an opportunity to link them to other resources. If participants report health concerns they will be directed to contact their health care team.

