Treatment fidelity and protocol adherence: See Human Subjects and Clinical Trials Information Section 4.2.a.13 and 4.3 for complete details on intervention fidelity, participant adherence, and adherence measurement. The NIH Treatment Fidelity Workgroup statement will guide our fidelity plan and Co-PI [name] has experience implementing these guidelines in a previous RCT intervention with adolescents undergoing blood and marrow transplant. Fidelity will be enhanced by the InquistHealth Mentor1to1™ platform which enables masked, direct voice communication; facilitates continuity of relationship between the AYA and peer coach; and allows for the systematic tracking of phone- and text-based interactions. After the call, the platform facilitates scheduling upcoming calls, automates text message and e-mail reminders, and allows for user-initiated text messaging between calls. Since all calls are facilitated through the platform, the system automatically tracks call length and frequency, and records these interactions. AYA engagement will be tracked and quantified by the number of contacts and average length of contacts time per week. These two numbers will be aggregated and plotted for each AYA. Together with weekly content analyses of a random selection of two calls and text messages from each coach, we will monitor AYA engagement and during biweekly coach training sessions address problems that arise. Fidelity will be assessed by examining peer

coach engagement and content of the call recordings. Peer coach engagement will be evaluated using the aggregated number of contacts and length of contact time for each of the 12-15 coaches. This will allow us to assess the extent to which coaches are engaged and to explore the reasons for increases or decreases in engagement. These evaluations will be performed weekly and feedback given to the peer coaches at the biweekly training sessions so that adjustments to the content/direction of the calls and text messages may be made by the coach at the subsequent call. A log will be kept of these assessments and any subsequent adjustments.

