**Aim 1 Efficacy Analyses.** To test the efficacy of the PICASO compared to the attention control condition on the primary and secondary outcomes across the five assessment points (time), we will use a type of hierarchical mixed-effect model for longitudinal data known as random coefficients regression models (RRM) to evaluate group differences in the trajectory of change in each outcome across time. Fixed effects will be group, time, group-by-time, while random effects will be participant and participant-by-time. Potential covariates will be included as fixed effects and will be retained in the final model only if significant at the 0.05 level. When needed, the model will be fitted for any non-linear temporal effects observed. The assumption of data missing at random will be evaluated, and imputation for missing data will be applied when appropriate. Descriptive statistics will be used summarize the unadjusted and adjusted means at each assessment point. If there is a significant group-by-time interaction, *a posteriori* contrasts will be performed to compare the two groups at each time point. For each outcome, the primary analysis will be an intention-to-treat (ITT) analysis in which all AYAs randomized will be included in the analysis. Supplemental analyses will be conducted on those AYAs who complete the 12-month assessment. Both ITT and completers' results will be reported.

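### The primary model has no coach term, although 150 PICASO participants share 12 to 15 coaches and controls have none; the group-by-time standard error is too small if change correlates within coach.

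*Combined protocol and SAP*

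**What the plan says.** The Aim 1 Efficacy Analyses specify a random coefficients regression: "Fixed effects will be group, time, group-by-time, while random effects will be participant and participant-by-time". Other covariates stay only if significant at 0.05. Section 3.C.8 (Sample Size and Power Considerations) assumes d = 0.50, a two-sided 0.05 test, up to 20% attrition and correlation within participants. It names no correlation within coaches.

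Section 3.D.4.a describes how the intervention is delivered. The trial will employ 12 to 15 "peer coaches who represent the condition categories (see Table 5"). On matching it says: "Each AYA will be matched with a coach, based on membership in 1 of 3 condition categories". The platform is valued because it "facilitates continuity of relationship between the AYA and peer coach". Table 5 gives participants and coaches by category; the largest is "70 PICASO 35 control", with 5 to 6 coaches. Randomisation is individual and stratified: "While stratifying on condition category, a 2:1 treatment allocation will be applied". Controls receive a newsletter and "a monthly phone call from study staff to ensure receipt of the newsletter", with no coach.

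In the quantitative plan, coaches appear only in the descriptive statistics and in fidelity monitoring, which uses "the aggregated number of contacts and length of contact time for each of the 12-15 coaches".

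**The concern.** This is a partially nested design: one arm is clustered by coach and the other is not. The coach delivers the intervention for a year, and the content is nondirective and tailored, so some coaches may well achieve more change than others. If so, slopes that share a coach are positively correlated. A model with participant-level random effects only counts them as independent, so the group-by-time p-value is too small and the 95% interval too narrow.

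The null hypothesis at risk is an average effect of zero while coaches differ in their effect. If no coach has any effect, the ICC is zero and the test keeps its level. Interval coverage suffers whenever coaches differ, whatever the average effect. That matters because the plan relies on effect sizes with 95% intervals to judge clinical significance, and because neither primary outcome has an alpha adjustment that could absorb some inflation.

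**Working it through.** **Inputs from the plan.** 150 PICASO and 75 control; d = 0.50 (SD 1); two-sided 0.05; 20% attrition leaves 120 and 60 (section 3.C.8). Coaches per category 4-5, 5-6 and 3-4 for 50, 70 and 30 PICASO participants (Table 5).

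**Assumptions.** ICC 0 to 0.10, defined as the between-coach share of variance in participants' estimated slopes. Equal loads within category.

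**1. The plan's own power.** SE = √(1/n_T + 1/n_C).
- 150/75: SE = √0.02 = 0.1414; power = Φ(0.5/0.1414 − 1.96) = 94.2% (noncentral t 94.1%).
- 120/60: SE = √0.025 = 0.1581; power = Φ(0.5/0.1581 − 1.96) = 88.5% (noncentral t 88.2%).

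The claim of at least 80% is met as a floor. The exact calculation cannot be repeated, because the correlation values used are not given.

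**2. Coach loads.**
- 12 coaches: 4 with 12.5, 5 with 14, 3 with 10. Σm²/150 = (625 + 980 + 300)/150 = 12.70.
- 15 coaches: 5 with 10, 6 with 11.67, 4 with 7.5. Σm²/150 = (500 + 816.7 + 225)/150 = 10.28.

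**3. Design effect, PICASO arm only.** Deff = 1 + (Σm²/150 − 1) × ICC. The correct variance is Deff/150 + 1/75; the model uses 1/150 + 1/75 = 0.02. Example, 12 coaches at ICC 0.05: Deff = 1 + 11.70 × 0.05 = 1.585; variance = 0.01057 + 0.01333 = 0.0239; SE ratio = √(0.0239/0.02) = 1.093.

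**4. True type I error** = 2 × [1 − Φ(1.96 / SE ratio)]. Each cell is 12 / 15 coaches.

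| ICC | Deff | SE ratio | Type I error |
|---|---|---|---|
| 0 | 1 / 1 | 1 / 1 | 0.050 / 0.050 |
| 0.01 | 1.117 / 1.093 | 1.019 / 1.015 | 0.054 / 0.054 |
| 0.02 | 1.234 / 1.186 | 1.038 / 1.030 | 0.059 / 0.057 |
| 0.05 | 1.585 / 1.464 | 1.093 / 1.075 | 0.073 / 0.068 |
| 0.10 | 2.170 / 1.928 | 1.179 / 1.144 | 0.096 / 0.087 |

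Coverage is one minus the last column: about 93% at ICC 0.05 and 90 to 91% at 0.10.

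**5. Power with the correct SE** (noncentral t, Satterthwaite degrees of freedom with coaches − 1 for the PICASO part).
- 150/75: 89 to 90% at ICC 0.05; 83 to 86% at 0.10.
- 120/60: 82 to 84% at ICC 0.05; 77 to 80% at 0.10.

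**6. Simulation check.** 20,000 trials per setting on per-person slopes, which is equivalent to the group-by-time test with balanced, complete data.
- With category as a fixed effect and no coach term, type I error at ICC 0 / 0.01 / 0.05 / 0.10 was 0.050 / 0.054 / 0.074 / 0.096 (12 coaches) and 0.053 / 0.054 / 0.069 / 0.088 (15 coaches).
- A separate simulation with 12 equally loaded coaches gave a mean model SE of 0.141 against a true SD of 0.154 at ICC 0.05 (type I error 0.073), and 0.141 against 0.168 at ICC 0.10 (0.099).

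**7. Category without coach effects.** Variation due only to condition category, the randomisation stratum, gave 0.043 to 0.046, so it does not inflate the error.

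**The case against.** The strongest reply is that the harm depends on a number the documents do not give. At ICC 0.01 to 0.02 the error rate is 0.054 to 0.059, which is negligible, and the common training, semi-monthly supervision and weekly call review are meant to make coaches alike. This stands as a limit on size. It does not justify a model that neither allows for the correlation nor estimates it.

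Other points also reduce the figures:

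- **Definition of the ICC.** It applies here to estimated slopes, which include measurement error. If a true-slope ICC were 0.10 and slope reliability 0.3 to 0.7 (assumed), the error rate with 12 coaches would be 0.064 to 0.082; at a true-slope ICC of 0.05, 0.057 to 0.066.
- **Category is not in the stated model.** Leaving out a stratification factor that affects slopes makes the test conservative. If category explains an assumed 5 to 10% of slope variance, the error rate falls to 0.056-0.067 at ICC 0.05 and 0.075-0.090 at 0.10, and the inflation can cancel near ICC 0.02. However, section 3.D.3.c itself reports more variation within diagnostic groups than between them, and relying on two errors to cancel is not a plan.
- **Fixed or random coaches.** If inference is limited to the coaches employed, their differences are fixed and the standard error is not too small on this account. Sections 3.C.9 and 3.C.11 claim generalisability and aim at wide deployment, which means other coaches, so random coaches fit the plan's purpose.
- **Power.** The 80% claim largely survives. At ICC 0.10 with the 90% retention expected in section 3.D.3.b, power is 80 to 83%.
- **Sections not seen.** The cross-referenced Human Subjects and Clinical Trials Information sections were not available. If they contain a coach term, the Aim 1 text must be reconciled with them.

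**Conclusion.** The concern holds. The design is partially nested and the stated model ignores it; that much is certain from the text. Any positive within-coach correlation of slopes makes the group-by-time standard error too small, apart from a partial offset if category also drives slopes and is left out of the model.

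The size is conditional on the ICC: trivial at 0.01 to 0.02 and material at 0.05 to 0.10, where a nominal 0.05 test runs at about 0.07 to 0.10. These figures assume full enrolment, 12 to 15 coaches, equal loads within category, coaches regarded as a sample, and an ICC on estimated slopes. This is mainly a problem of type I error and interval coverage. The stated power holds to about ICC 0.05 and is borderline or lost only near 0.10 with the full 20% attrition. It should be fixed before the analysis is locked, because the remedy is cheap.

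**What to change.** In the Aim 1 model:

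- Add a coach-by-time random effect for the PICASO arm only, plus a coach intercept if it can be estimated.
- Include condition category and category-by-time as fixed effects, so that category differences are not counted as coach variance.
- Use Satterthwaite or Kenward-Roger degrees of freedom.
- Prespecify a fallback for non-convergence or a zero coach variance: first drop the coach intercept, then use small-sample-corrected (CR2) cluster-robust standard errors with coach as the cluster and each control as a singleton.
- State how a participant who changes coach is analysed, for example under the first assigned coach.
- Say that coaches are regarded as a sample, define the coach ICC on participant slopes, and report it with its interval.
- In section 3.C.8, give power over ICC 0 to 0.10 for 12 to 15 coaches.

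Carrying the term into the exploratory Aim 2 models is desirable but not essential.

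In the slope simulation the partially nested REML model held type I error at 0.043 to 0.056, the same model with CR2 substituted at zero variance at 0.049 to 0.056, and CR2 alone at 0.050 to 0.054. CR2 throughout is therefore a simpler acceptable choice. The full five-visit model with missing data was not simulated with enough replicates to be informative.

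**Cost.** SAP wording and a coach identifier in the analysis file; contacts are already totalled by coach. Intervals become slightly wider and stated power lower. With 12 to 15 clusters the coach variance is imprecise: it was estimated at zero in 46 to 47% of simulated trials at ICC 0.01, 21 to 22% at 0.05 and 8% at 0.10, so the fallback will often be used.

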#### Aim 1 and 2 Analysis Plan

Descriptive statistics will be used to detail the sample characteristics of the (a) coaches and randomized AYAs and (b) detail the study outcomes for the AYAs at the five-assessment point (baseline, 3-, 6-, 9-, 12-months post randomization). Non-directional statistical tests will be performed, with the significance level set at 0.05 for each test. The significance level will not be adjusted for multiple outcomes and tests (see Power section below). Estimated effect sizes and their 95% confidence intervals (CI) will be reported to address magnitude of effect and clinical significance for the efficacy and moderator analyses (Aims 1 and 2, respectively).

**AYA Sample Characteristics.** Chi-square/Fisher's Exact Tests for categorical variables and General Linear Models (GLM) for continuous measures will be used to test for group (PICASO vs attention control) differences in the baseline demographic and clinical characteristics as well as baseline outcome measures for the AYAs. A GLM approach, which calculates least square means to adjust for unequal sample sizes, will be used to test for between-group differences in the means for continuous measures. Any significant between-group difference in a baseline characteristic detected will be evaluated as a potential covariate in the efficacy analyses

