### **3.C.8. Sample Size and Power Considerations**

A target sample size of 225 AYAs (PICASO: N=150; control: N=75) will be provide at least 80% statistical power to address the efficacy of PICASO compared to the attention control condition (Aim 1) and will provide sufficient heterogeneity to obtain reliable estimates of effect sizes for the exploratory moderator analyses. Using PASS software (NCSS LLC, Kaysville, UT), the sample size determination for the two primary outcomes was based on the following assumptions: (a) mixed-effects trajectory analyses using RRMs; (b) two-tailed tests with significance set at 0.05 per test; and (c) medium effects (Cohen  $d$  equivalent of 0.50); and (d) unstructured within-subjects correlation patterns over time. The significance level of 0.05 will not be adjusted for evaluating two primary outcomes. Although the mixed-effects models allow for data missing at random, the sample size of 225 takes into account an attrition rate of up to 20% over time, and thus, should provide 80% power for both the ITT and completers' analyses of the two primary outcomes.

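### The Aim 1 model gives each arm its own baseline mean although randomisation follows baseline; a common baseline mean would gain precision at no cost

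*Combined protocol and SAP*

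**What the plan says.** The Aim 1 Efficacy Analyses paragraph fits a random-coefficients model to each outcome at baseline and 3, 6, 9 and 12 months. Its terms are: "Fixed effects will be group, time, group-by-time, while random effects will be participant and participant-by-time". If the interaction is significant, the two groups are then compared at each time point.

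Baseline precedes allocation. Section 3.D.4.a states: "On completion of baseline data collection, AYAs will be randomized".

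The plan states no common-baseline constraint and no prespecified baseline covariate. The only route to one is conditional. The AYA Sample Characteristics paragraph tests the arms for differences in demographic and clinical characteristics "as well as baseline outcome measures for the AYAs". A significant difference makes the variable a candidate covariate, and the Aim 1 paragraph keeps it only if it is significant at 0.05.

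Section 3.C.8 claims at least 80% power for an effect of d = 0.50, with "two-tailed tests with significance set at 0.05 per test" and up to 20% attrition. It describes the correlations only as "unstructured within-subjects correlation patterns over time", without values.

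**The concern.** With baseline in the response vector, the group main effect is the arm difference at time zero. Randomisation after baseline makes that difference zero in expectation, so the model spends a parameter on a quantity already known. This has three consequences.

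- Group-by-time becomes a pure change comparison. It uses baseline, but with less precision than a model that knows the arms start from one mean.
- The contrast at each time point is group plus group-by-time, a difference in level without baseline adjustment. Section 3.D.4.a defines the primary outcomes as post-intervention PIH and PAM scores, so the month-12 contrast is what many readers will look for.
- The conditional covariate rule does not repair this. Under randomisation it is triggered by chance in about 5% of trials per outcome. It depends on the data, and it puts the same score on both sides of the model.

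Precision on both primary outcomes is at stake, as is a clear statement in advance of how baseline is handled.

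**Working it through.** **Stated power.** Inputs from section 3.C.8: d = 0.50, two-sided 0.05, 150/75, 20% attrition (leaving 120/60). On a simple two-mean basis:

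- Control n for 80% = (1.960 + 0.842)² × (1 + 1/2) / 0.50² = 47.1, so 48 + 96 = 144, and 144/0.8 = 180 with attrition.
- At 120/60: SE = √(1/120 + 1/60) = 0.158; 0.50/0.158 = 3.162; power = Φ(3.162 − 1.960) = 88.5%.
- At 150/75: power = 94.2%.

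At least 80% therefore holds as a floor on this basis. The plan's own calculation cannot be reproduced, because its correlations are not given.

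**Variances under the planned model.** Assumptions: linear time scaled 0 to 1 over 12 months; five complete visits; baseline variance 1; ICC = share of baseline variance due to participant; s = random-slope SD in baseline SDs per 12 months; r = intercept-slope correlation; 120/60, so the allocation factor is 1/120 + 1/60 = 0.025. The visits have mean 0.5 and sum of squares 0.625. For one participant's fitted line:

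- V00 (baseline level) = ICC + 0.6(1 − ICC)
- V11 (slope) = s² + 1.6(1 − ICC)
- V01 (covariance) = r·s·√ICC − 0.8(1 − ICC)

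Multiply each of the following by 0.025:

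- group-by-time, free baseline means: V11
- month-12 contrast, free baseline means: V00 + 2V01 + V11
- either quantity, common baseline mean: V11 − V01²/V00

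Worked case, ICC 0.5 and s = 0: V00 = 0.80, V11 = 0.80, V01 = −0.40. Free: 0.80 × 0.025 = 0.0200 for both quantities. Common mean: (0.80 − 0.16/0.80) × 0.025 = 0.0150. The ratio is 1.33, and power at d = 0.50 goes from 94.2% to 98.3%.

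| ICC, s, r | group-by-time, free | month-12, free | common mean | ratio, group-by-time | ratio, month-12 |
|---|---|---|---|---|---|
| 0.4, 0.3, −0.3 | 0.0262 | 0.0184 | 0.0168 | 1.57 | 1.10 |
| 0.4, 0.7, −0.3 | 0.0362 | 0.0246 | 0.0239 | 1.52 | 1.03 |
| 0.5, 0, – | 0.0200 | 0.0200 | 0.0150 | 1.33 | 1.33 |
| 0.5, 0.5, 0 | 0.0263 | 0.0262 | 0.0213 | 1.24 | 1.24 |
| 0.7, 0, – | 0.0120 | 0.0220 | 0.0104 | 1.16 | 2.12 |
| 0.7, 0.7, 0.3 | 0.0243 | 0.0430 | 0.0241 | 1.00 | 1.78 |

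Over the full grid (ICC 0.4-0.7, s 0-0.7, r −0.3 to 0.3) the ratio runs from 1.00 to 1.57 for group-by-time and from 1.03 to 2.12 for the month-12 contrast. The planned model is never the more precise one.

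**Share of a chance baseline difference carried into the month-12 contrast.** The baseline visit has weight 0.2 − 0.4 = −0.2 in the fitted month-12 value, so the share is ICC − 0.2(1 − ICC) + r·s·√ICC. With s = 0 it is 28%, 40% and 52% at ICC 0.4, 0.5 and 0.6. The grid extremes are 0.28 − 0.13 = 15% (ICC 0.4, s 0.7, r −0.3) and 0.64 + 0.18 = 82% (ICC 0.7, s 0.7, r 0.3). With a common baseline mean the expected share is zero.

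**The conditional covariate.** A baseline score entered as a fixed effect shifts each participant's level, not the slope. With complete data the group-by-time estimate therefore does not move. In two simulated complete data sets it was identical with and without the covariate (−0.01203 and 0.18137), while its standard error rose from 0.142 to 0.154 and from 0.138 to 0.151.

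**The case against.** Group, time and group-by-time is a conventional growth model. Four stronger readings are tempting, and the documents support none of them.

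- *That the deciding test ignores baseline.* It does not. Baseline is one of the five responses, so group-by-time compares change and removes the level difference. Its fault is inefficiency.
- *That the month-12 contrast carries all of a chance imbalance.* It carries about 15-82% under the assumptions above. The time-point contrasts are also secondary, since they follow only a significant interaction.
- *That the 80% power claim fails.* With equal correlations of 0.2, 0.3, 0.4 and 0.5 across the five visits, the planned model gives about 80%, 85%, 90% and 94%, against 97%, 97%, 97% and 98% with a common baseline mean. Large slope variance can take the planned model below 80% (74.7% at ICC 0.4, s = 0.7). That value is assumed, and there the common-mean model gives only about 80-90%.
- *That type I error is inflated.* Over all randomisations the group-by-time estimate is unbiased and, with a correctly specified covariance, the test holds its level. Error rises only conditionally, in the few trials where baseline happens to differ significantly.

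Two further limits stand. The covariate result is exact only for complete data, while the plan allows up to 20% attrition. A baseline covariate would also change the group term, and so the time-point contrasts.

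What survives is narrower: the free baseline difference gains nothing in a trial randomised after baseline, and the plan's remedy for imbalance depends on a significance test.

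**Conclusion.** The point holds as an efficiency and prespecification improvement. The planned group-by-time test is valid but less precise than it could be, and the time-point contrasts lack baseline adjustment. Under the stated assumptions the excess variance is 0-57% for group-by-time and 3-112% for the month-12 contrast. Where the group-by-time gain is nil (ICC 0.7, s = 0.7, r = 0.3), the month-12 contrast variance is still 78% larger. The size rests wholly on assumed correlations, linear time and complete visits, because the documents give no values for PIH or PAM. The direction does not: it follows from randomising after baseline.

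**What to change.** In the Aim 1 Efficacy Analyses paragraph, prespecify one common baseline mean: fixed effects time and group-by-time, no group main effect, baseline kept as the first response. Take the month-12 and other post-baseline contrasts from that model.

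An acceptable alternative is to model only the post-baseline responses, with the baseline score as a prespecified covariate. Participants with no post-baseline visit then contribute nothing unless imputed, so the first option fits the plan's intention-to-treat statement more directly.

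Under either option, state that an outcome's own baseline score is excluded from the significance-driven covariate rule in the AYA Sample Characteristics and Aim 1 paragraphs. It would also help to give, in section 3.C.8, the correlations behind the power figure.

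The cost is wording only. The first option has one parameter fewer, needs no new data and keeps all randomised participants. It should be settled before outcome data by arm are seen.
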